3.0 Animal Studies and Previous Human Studies

PRELIMINARY DATA

In a recently completed study designed to investigate the effects of a high fat diet on cardiometabolic outcomes in 144 obese adults ([name] and [name]), we found that 36 of 144 (25%) had a history of GERD symptoms and/or medication use at least once a week at baseline.

Closer assessment of subjects' dietary intakes revealed that subjects with GERD had significantly higher energy intakes, simple carbohydrate intakes (total sugar), sucrose intakes, and overall dietary glycemic load – but not higher dietary fat or protein intakes (Table 1). In addition, there was no difference in subjects' intakes of caffeine, as well as alcohol, chocolate or other dietary factors commonly associated with GERD (data not shown). Notably, in regression modeling, total sugar intake was a strong predictor of having GERD symptoms ($p = 0.007$).

Table 1. Baseline Demographic and Nutrient Differences			
	GERD (N = 36)	No GERD (N = 108)	P-Value
Demographics			
Age (y)	39.2 ± 5.9	35.9 ± 6.9	0.011
Race			0.039
Caucasian	30 (83%)	70 (65%)	
African American	6 (17%)	38 (35%)	
Nutrients (per day)			
Amount of Food (g)	2675.7 ± 610.1	2778.1 ± 815.9	0.491
Energy (kcal)	2103.1 ± 435.2	1840.1 ± 435.0	0.002
Fat (% kcal)	37.2 ± 6.0	38.7 ± 7.8	0.311
Protein (% kcal)	15.6 ± 2.9	16.9 ± 4.6	0.095
Carbohydrate (% kcal)	46.5 ± 6.1	43.9 ± 9.6	0.135
Total Fiber (g)	16.8 ± 6.5	15.2 ± 5.8	0.177
Soluble Fiber (g)	5.9 ± 2.8	5.0 ± 2.1	0.037
Total Sugar (g)	101.6 ± 50.3	82.5 ± 40.9	0.024
Sucrose (g)	52.8 ± 37.8	36.6 ± 23.5	0.003
Fructose (g)	16.3 ± 12.6	16.8 ± 12.1	0.821
Glycemic Load	198.9 ± 51.4	166.2 ± 59.1	0.004
Caffeine (mg)	160.1 ± 112.6	133.7 ± 102.6	0.195
HOMA-IR (score)	2.9 ± 2.5	2.5 ± 2.0	0.278

In the subjects with GERD, all GERD symptoms and medication use had resolved by completion of the 9-week low carbohydrate / high fat diet intervention. While there was no difference in the average amount of food consumed per day between subjects with GERD versus those without, the subjects with GERD did have significantly greater reductions in energy intakes, sucrose intakes, and overall dietary glycemic load (Table 2).

Table 2. At Week 9 of Low Carbohydrate / High Fat Diet

	GERD	No GERD	
Baseline GERD Status	N = 36	N = 108	
GERD Resolved	36/36	n/a	P-Value
Amount of Food (grams)	-141.8 ± 573.7	-179.2 ± 775.5	0.821
Energy (kcal)	-372.7 ± 400.1	-144.7 ± 425.4	0.018
Fat (% kcal)	12.9 ± 6.3	10.9 ± 8.2	0.239
Protein (% kcal)	4.8 ± 3.7	4.5 ± 4.5	0.792
Carbohydrate (% kcal)	-17.5 ± 6.2	-15.3 ± 8.9	0.241
Total Fiber (g)	3.3 ± 8.4	5.2 ± 5.7	0.211
Soluble Fiber (g)	2.5 ± 2.9	3.6 ± 2.7	0.114
Total Sugar (g)	-62.1 ± 44.0	-43.4 ± 42.1	0.057
Sucrose (g)	-37.5 ± 28.2	-22.3 ± 25.4	0.013
Fructose (g)	-9.6 ± 12.8	-8.6 ± 10.9	0.711
Glycemic Load	82.5 ± 30.1	62.2 ± 39.9	0.018
Caffeine (mg)	117.2 ± 92.9	101.9 ± 106.8	0.513
HOMA-IR Score	-1.1 ± 1.8	-0.3 ± 1.2	0.018

4.0 Inclusion/Exclusion Criteria

As race, age and gender have not been shown to affect GERD status, we will enroll any interested patient who meets the following criteria:

Inclusion Criteria	Exclusion Criteria

 • Age: ≥ 21 years • BMI: 25-45 kg/m² • GERD diagnosis in the medical record which will be confirmed by study baseline pH testing, if baseline pH is not < 4.0 for ≥ 5.5% of time during 24hr testing, subject will be excluded. 	
 • History of type 1 diabetes • Hernia > 5 cm • Current or remote history of esophageal stricture • Gastroparesis • Extra-esophageal GERD • Barrett's esophagus or Esophageal adenocarcinoma • History of gastric or bariatric or esophageal surgery, radiation or cancer • History of gastrointestinal malabsorption • Alcohol averaging > 2 drinks per day during past 3 months • Pregnancy / Lactation

5.0 Screening & Enrollment

All recruitment procedures will be IRB-approved. Study participants will be recruited from the VA clinic patient population under the guidance of [name], study co-investigator and VA gastroenterologist. We anticipate that the majority of patients will be recruited from primary care clinics. We will also engage the VA pharmacy service, utilizing the robust electronic medical record system, to identify patients currently on prescriptions for GERD and who have relevant diagnoses (i.e., ICD-9 codes 530.81 and 530.11) and are scheduled to come to a given clinic on a specific day. Our study nurse will work closely with charge nurses and clinic staff to identify potential subjects. Upon review of pharmaco-economic data from TVHS, we have identified that 45% of the total TVHS veteran population of 65,000 are obese and that there are currently 19,094 patients on PPIs. In the course of clinic interactions, clinic staff will determine whether a patient has general interest in participating in this study (i.e., provides verbal consent to be approached by study nurse for full description of study procedures). From our more intensive GI clinical trials, we currently enroll 30-35% of patients approached (personal communication [name]).

Based upon prior published studies in VA facilities, successful recruitment for patients with GERD has been documented from the following clinical settings: internal medicine/primary care clinics, emergency department, and lastly, general GI clinics. We will initially focus our recruiting efforts on the Nashville campus, the Charlotte Avenue primary care clinic facility, and at the Murfreesboro Alvin York campus, as a high volume of primary and specialty care occurs at these three sites.

A secondary recruitment strategy will involve the placement of IRB approved posters and brochures in the waiting areas of target clinics with basic study information and a contact line for potential subjects to register potential interest. We anticipate screening 6-10 subjects per week for eligibility. We will perform a baseline pH study after consent. Based on clinical experience, we expect 15-20% of Vets diagnosed with GERD will be screen failures as they will not have pH < 4.0 for > 5.5% of a 24-hour period (personal communications [name] & [name]). These 15-20% will be excluded from study as the underlying hypothesis is that low carbohydrate / low sugar diet will reduce % time with pH < 4.0 to < 5.5%. Thus, we expect to meet our targeted enrollment of 1-2 subjects per week, which is based on the ability to schedule this number of patients in the GI clinic for pH testing. Thus, our recruitment and enrollment goals appear to be highly feasible with such a huge patient population at TVHS (currently a total of 65,000 patients; 29,250 of whom are obese, and 19,100 are currently on PPIs, thus ~65% of these obese vets have GERD).

6.0 Study Procedures

Randomization: 200 subjects (50 per arm) will be randomized to diet treatment arm. we have reviewed drop-out rate from clinical trials in gastroenterology in this population ([name] and [name] personal communications), which would predict a 20% drop out rate. The number of subjects to enroll reflects a completion rate of 80% (enroll 50 per arm = 200 subjects x 0.80 = 160 completers). In considering that drop out could be higher, we will now include subjects in our final analyses who notify us they are dropping-out between weeks 7-9 by asking them to return for a final visit at the time of drop-out (we do this regularly and get agreement from about 66% of subjects to return for a final testing session even if they are not continuing to wk 9). Randomization of subjects will be carried out using unified reproducible methods (i.e. saved random number seed) provided by the Biostatistician ([name]). We will use a permuted block randomization scheme, stratifying on gender to ensure this covariate is balanced

between randomization groups. The block size will be varied randomly. Treatment assignments will be contained in sealed, thick envelopes to be opened after informed consent is obtained.

Overall Schema:

Timepoint	Baseline	Day 1-7	End Wk 1	Day 8-57	Day 57-63	End Wk 9
Consent & Enrollment	X					
Randomization			X			
Bloodwork	X		X		X	X
Diet Intervention						
Off PPIs #1						
Clinical Testing #1				X		
Off PPIs #2						
Clinical Testing #2						X

Testing Procedures:

Baseline levels of all measures listed below will be obtained prior to study day 1.

PPIs will be stopped for 1 week, medications that affect gastric motility for 2 days, H₂RAs for 2 days, and antacids for 2 days - *prior to testing on study days 7 and 63. Additional blood work will be drawn on study day 57 for evaluation of levels prior to discontinuation of PPIs #2.*

Subjects will be instructed to stop eating and drinking, except water, at 10pm on the evening before each clinical testing day. Thus, subjects will arrive at the VA on study days 7 and 63 NPO. Subjects will be escorted by study staff from the VA to the Vanderbilt Clinical Research Center at 0700. Subjects will be admitted to a private outpatient room (has private bed and bathroom). An updated medical history will be obtained to ensure absence of recent/current illness. CRC nursing will obtain vital signs and perform the blood draw. As part of the blood draw, female subjects will have a pregnancy test (via serum βHCG). The study dietitian will perform anthropometric, body composition (DEXA), dietary and GERD symptom survey measures as described below. The subject will then be escorted by study nurse to the Vanderbilt GI Clinic for impedance monitoring and gastric emptying test procedures under the guidance of [name] (study co-investigator), as described below. Impedance monitoring will continue for a 24-hour period. Subjects will be provided with a meal that is consistent with the diet intervention and the treatment arm they are assigned to before being discharged home. The study nurse will telephone subjects in the early evening to assure no problems from study procedures have developed. Subjects will return to the VA to meet briefly with the study nurse on the day after clinical testing to allow data retrieval and return of impedance monitoring and gastric emptying equipment.

For these Testing Visits, at the end of study week 1 and study week 9, participants have the choice of staying overnight in a private room at the Vanderbilt Clinical Research Center for the 24-hour period of testing, or they can return to the Vanderbilt Digestive Disease clinic on the morning after the 24-hours of pH and SmartPill monitoring for the removal of the pH catheter and collection of the recording devices.

Measures: to be performed in the fasting state at baseline, end study week 1, pre/post study week 9

- **Bloodwork:**
 - **Glucose:** Plasma glucose concentration will be analyzed in triplicate via glucose oxidase method using a Beckman glucose analyzer at the VA Clinical Laboratory.
 - **Insulin:** Plasma insulin concentration will be shipped to LabCorp and analyzed by radioimmunoassay method.
 - **HOMA-IR:** Calculated from glucose and insulin values.
 - **Hormones:** Serum gastrin will be assayed at LabCorp. Glucagon and GLP-1 by Luminex multiplex assay at the Diabetes Hormone core lab. Serum ghrelin (active acylated form) by radioimmunoassay at the Diabetes Hormone core lab. While several other hormones are involved in gastric acid secretion and motility, we have chosen two key stimulators (gastrin and glucagon) and two key inhibitors (GLP-1 and ghrelin), as well as insulin, to investigate in this proposal utilizing a dietary intervention in obesity.
- **Anthropometrics:**
 - **Height** (m) and **Weight** (kg) measured on calibrated digital equipment will be used to calculate **BMI**.
 - **Waist Circumference** will be measured using a flexible tape at the level of the umbilicus.⁴⁵
- **Body Composition:** In addition to total and regional body composition (fat, lean and bone mass) obtained from the Lunar iDXA (GE Healthcare), we will use new technology recently acquired by VICTR to estimate visceral adipose tissue (VAT) – a possible risk factor for GERD.⁴⁶ This fully automated approach to capture VAT has been validated against CT⁴⁷ and offers several advantages to MRI or CT: fast, low cost, exposes one to less radiation, and makes serial measurements possible.
- **Metabolic Testing:** To capture a more objective measure of change in energy balance due to the dietary intervention, we will perform indirect calorimetry by metabolic cart while subjects are at the CRC on week 1 and 9.
- **24 hour urine collection:** To effectively measure how well the body processes food intake
- **Dietary Intake:** will be assessed via averaging three 24-hour diet recalls obtained at baseline and again within a 7-day window of each clinical testing visit (study weeks 1 and 9). Recalls will be performed by the Vanderbilt Nutrition and Diet Assessment Core using the USDA multi-pass methodology,^{48,49} a standardized script, and computer-generated prompts (NDS-R, v. 2013, Nutrition Coordinating Center, Minn, MN). We are familiar with underreporting especially in people with high BMI and use portion size tools and statistical methods to assure

data reliability. The 1st of 3 recalls will be in-person at the CRC, which allows training of subjects in the interview methodology.

- **Medication Use:** will be assessed by two methods: a) we will provide subjects with a notebook that includes daily logs for them to record medication type and amount; and b) weekly interview by study nurse. In addition, we now have bloodwork being drawn pre and post weeks 1 and 9 that will inform medication use by measurement of hormone levels, i.e., gastrin.
- **24-Hour Impedance Monitoring:** will be performed by using a combined MII-pH monitoring device (Sandhill Scientific Inc; Highlands Ranch, CO) comprising a data recorder (Sleuth System; Sandhill Scientific Inc) and a 2.1 mm diameter polyvinyl catheter embedded by one pH and 6 impedance sensors at predefined positions. The pH sensors are calibrated before placement using standardized buffer solutions at pH 4.0 and 7.0 per manufacturer. The catheter is placed intranasally so that the esophageal pH sensor is positioned 5-cm above the manometrically defined upper border of the lower esophageal sphincter (LES). Intraluminal impedance is measured at 3, 5, 7, 9, 15 and 17cm above the LES. Data sampling frequency for both impedance and pH sensors is 50 Hz. Data are downloaded from the recorder and analyzed using BioView Analysis software (Sandhill Scientific Inc). Reflux episodes are identified by computerized detection (Autoscan; Sandhill Scientific Inc.) of proximally directed decreases in impedance. Tracings are also manually reviewed by an experienced investigator ([name]) to confirm accuracy and correct errors. Total, upright and supine reflux events are recorded. Acid reflux events are defined as those with pH \leq 4 and non- or weakly acid reflux events are those occurring at pH $>$ 4.
- **Gastric Emptying:** Subjects will swallow an activated and calibrated SmartPill wireless pH, pressure and temperature capsule. The capsule houses sensors for pH, temperature and pressure. Shape and dimensions of the capsule are: cylindrical, 26.8mm long by 11.7mm in diameter. The capsule has a pH range of 0.5–9 with an accuracy of \pm 0.5 pH units. The pressure sensor has a pressure range of 0–350 mmHg with an accuracy of 5 mmHg below 100 mmHg and 10% at or above 100 mmHg. The temperature sensor has a range of 25–49 C, with an accuracy of \pm 1 C. Subjects ingest the capsule with 50 cm³ of water and afterwards begin eating a standard meal with an additional 120 cm³ of water. After activation and ingestion, the capsule signals are transmitted from within the GI tract and are captured by a receiving antenna incorporated into the receiver. The portable receiver worn by the subject receives and stores data which is downloaded to a PC computer. The transfer of data to the PC is accomplished via placement of the receiver in a docking station which provides an interface for data transmission to a computer as well as connections for battery charging. MotiliGI software (SmartPill, Inc.) loaded on the computer supports the data transfer, analysis of the recorded data, and displays the test results. Capsule gastric emptying time is defined as the duration of time from capsule ingestion to an abrupt pH rise (usually >3 pH units) from gastric baseline to a pH >4 as the capsule passes from the acidic antrum to the more alkaline duodenum.
- **GERD Symptoms:**

- **GERD Symptom Assessment Scale (GSAS)** will be used to measure the frequency, severity and distress for GERD symptoms. Internal consistency is >0.80 for symptom severity and distress scales. Validity, stability and sensitivity to change in symptom severity over time have been confirmed.^{17,50}
- **GERDQ** is a 6-item self-administered questionnaire designed for diagnosis and management of the GERD patient. It differentiates patients with occasional reflux symptoms from those with frequent symptoms. Two items measure impact of GERD symptoms on daily life and 4 items are used to monitor and evaluate the impact of treatment over time.¹⁸

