
Choice of Objective Disease Measures: As described above in section 1.1, we will employ impedance pH monitoring to determine acid and non-acid reflux events over a 24-hour period. This will allow data collection for *our primary outcome, percent of time with pH < 4.0*, as well as the other 5 measures that comprise the Johnson-DeMeester score.¹⁵ For motility, we will use the the SmartPill monitoring system, which measures whole and regional gut transit times. Kuo et al³⁸ and Sarosiek et al³⁹ describe sensitivity and specificity for the SmartPill. SmartPill gastric emptying time was compared to gastric emptying scintigraphy (GES). Correlation between SmartPill and GES was 0.73, the

ROC curves between healthy subjects and gastroparetics was 0.83 for SmartPill and 0.82 for GES, and the sensitivity/specificity for diagnosing gastroparetics for SmartPill was 0.65 / 0.87 and for GES was 0.44 / 0.93. In addition, Maqbool et al⁴⁰ showed correlation between SmartPill transit time and scintigraphy was 0.95 at 120 mins and 0.73 at 240 mins. Finally, Timm et al⁴¹ showed SmartPill assesses transit time in a within-subjects dietary crossover trial, where the amount of food was controlled but fiber source differed, indicating reliability for assessing dietary carbohydrate changes. Delayed gastric emptying is implicated in such disorders as idiopathic and diabetic gastroparesis and functional non-ulcer dyspepsia. The primary outcome measure from this test will be gastric emptying time. We recognize that a possible limitation of our proposed study is that we are not performing endoscopy to determine mucosal damage. While we will be using the clinical gold standard assessment of pH and reflux, it is well beyond the scope and capacity in this study to perform endoscopic assessments of mucosal health. Demonstration of a strong effect of the dietary intervention on GERD could prompt the development of future more invasive studies to examine such effects.

Choice of Subjective Disease Measures: As there are ~20 instruments to assess GERD symptoms, most of which were evaluated in a systematic review,¹⁶ we have chosen two scales, the GSAS¹⁷ and the GERDQ,¹⁸ that have strong sensitivity and also have both item and context validity (both are more fully discussed above in section A.1., and in the Measures section i below).

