Diets: We have extensive experience designing, prescribing and assessing diets.^{42,43} At baseline, dietary intake will be assessed by the Vanderbilt Nutrition and Diet Assessment Core (full methods described under Measures below). Energy content of daily intake will be estimated based on the individual's daily energy requirement using the Harris Benedict Equation with an activity factor of 1.2.⁴⁴ By doing so, calorie level will be individualized to assure weight maintenance during the study. In addition to being weighed at each clinical testing visit, body composition will be evaluated via DEXA scans at clinical testing visit to assure no changes in either total fat or truncal fat mass influence study results.

Subjects will be provided with daily meal plans that adhere to the composition of the treatment arm to which the subject is randomized. Meal plans will be developed by the co-Investigator ([name]) using NDS-R software (NDS-R version 2013, Nutrition Coordinating Center, Minn, MN) and instructed to subjects by the study dietitian at the end of study week 1 (see Schema below). To manipulate the carbohydrate amount (high vs low), we will alter the fat content of the diet. There will be no difference among diets in protein content. To manipulate type of carbohydrate (complex vs simple), we will provide instructions, the written meal plan, and a comprehensive list of which carbohydrate foods the subject can/can't consume.

To clearly delineate, simple carbohydrates are defined as those carbohydrates classified as mono- or di-saccharides, meaning they have one (glucose, galactose, fructose) or two (sucrose, lactose, maltose, trehalose) sugar units. Major sources of simple carbohydrates (or "sugars") are: soft drinks, cakes, cookies, pies, fruit punch, sweet tea, candy, table sugar, and syrups. Complex carbohydrates are also known as "starches" and consist of the oligo- and poly-saccharides, meaning they have 3 or more sugar units. Major sources of complex carbohydrates (or "starches") are: grains, cereals, legumes, corn, popcorn, pasta, rice, potatoes and vegetables. We recognize that major sources of both simple and complex carbohydrates have components of both and we are able to quantify these within a food using the NDS-R software.

All meal plans will provide 3 meals and 2 snacks per day that meet the macronutrient composition and the diet treatment arm:

- HTHS Diet: 55% total CHO (½ complex / ½ simple CHO), 30% fat, 15% protein

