Aim 1: *To determine effects of dietary carbohydrate consumed (amount and type) on percent time with esophageal pH < 4.0, as well as number of reflux episodes, GERD symptoms and GERD medication use, in 200 obese veterans who have chronic high frequency of GERD symptoms.* To meet this aim we will use a randomized controlled trial in which we manipulate amount of total and simple dietary carbohydrate intake for duration of 9 weeks.

Aim 2: To assess associations between GERD resolution variables and factors related to potential mechanisms by which modifying dietary carbohydrate intake could resolve/reduce GERD in obese veterans.

2a: We will investigate associations related to whether the effect is nutritionally mediated by measuring change in dietary fiber load and dietary glycemic load, and thus, whether these changes are related to improved gastric acid secretion (% time pH < 4), gastric motility, and/or the other parameters that comprise the Johnson-DeMeester score.

2b: We will also investigate whether effects are associated with changes in the hormonal milieu by measuring hormonal response of gastrin, glucagon, GLP-1, ghrelin and insulin, which could potentially influence gastric acid secretion, gastric motility and/or lower esophageal sphincter function.

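### The dietitian who teaches the randomized diet also performs the GERD symptom surveys, which leaves the self-reported Aim 1 symptom outcomes open to avoidable assessor influence, clearly so at day 63

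*Combined protocol and SAP*

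**What the plan says.** **Who teaches the diet.** Section 2.2 (Diets) states: "Subjects will be provided with daily meal plans that adhere to the composition of the treatment arm to which the subject is randomized". Those plans are "instructed to subjects by the study dietitian at the end of study week 1".

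**Who runs the symptom surveys.** Section 6.0 (Testing Procedures) states: "The study dietitian will perform anthropometric, body composition (DEXA), dietary and GERD symptom survey measures as described below". The testing visits fall on study days 7 and 63 ("For these Testing Visits, at the end of study week 1 and study week 9"). The same section requires baseline values of all measures before study day 1.

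**What the surveys are.** Section 6.0 (Measures, GERD Symptoms) names two scales. The GSAS "will be used to measure the frequency, severity and distress for GERD symptoms", with no mode of administration given. The GERDQ "is a 6-item self-administered questionnaire designed for diagnosis and management of the GERD patient".

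**Where they count.** Aim 1 (section 2.3) covers percent time with pH < 4.0, "as well as number of reflux episodes, GERD symptoms and GERD medication use". Section 2.1 names "our primary outcome, percent of time with pH < 4.0" as the primary outcome.

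**The concern.** Teaching an arm-specific diet requires knowing the arm. If the person who taught it also performs the survey, the subject reports symptoms to someone who is identified with the diet and may be seen as wanting it to work. Answers can then drift toward what seems expected, and the way items are presented or clarified can drift too.

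The team's expectation is strong and has a direction. The specific hypothesis in section 2.3 is that cutting simple carbohydrate will reduce or resolve symptoms, and section 3.0 reports resolution in 36 of 36 subjects with GERD. A reporting shift that differed between arms would look like a diet effect on symptoms. Section 10.0 contains nothing that could detect it or take it out: the models there concern percent time pH < 4, PPI dose and weight.

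**Working it through.** No figure in the plan is in dispute, so the check sets the passages side by side.

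1. **Same role?** Section 2.2 gives diet instruction to the study dietitian, and section 6.0 gives the symptom surveys to the study dietitian. Both use the singular. Two different dietitians are not excluded, but nothing provides for them.

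2. **Does that person know the arm?** Yes. The meal plan taught is the one for the randomized arm.

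3. **Is there a safeguard after assignment?** None is described. The sealed envelopes in section 6.0 (Randomization) protect the assignment step only. No blinding of subjects, dietitian or assessors appears.

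4. **At which visits does it apply?**
   - Baseline: before randomization, so not exposed.
   - Day 7: the Overall Schema places randomization at the end of week 1, section 2.2 places diet instruction at the same point, and the survey is taken at that visit. The envelope is to be opened after consent, which does not settle the order. The arm must be known before discharge, because the subject then receives a meal matching it, but the plan does not say whether it is known when the survey is taken.
   - Day 63: clearly after randomization and teaching, so exposed.

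5. **Which scale?** The dietitian's tasks are to be done as described later in the section. For the GERDQ, that description is self-administration. For the GSAS, it is silent on mode. The GSAS is therefore the more exposed of the two.

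6. **Which outcomes are outside the concern?**
   - Percent time pH < 4.0 is recorded by the catheter system.
   - Reflux episodes are detected by software, with manual review of the tracings by an investigator.
   - Medication use comes from subject logs and a weekly study-nurse interview.

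   The dietitian collects none of these.

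7. **How large could the bias be?** It cannot be computed. The plan gives no SD, effect size or power for the GSAS or GERDQ.

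**The case against.** The strongest reply has four parts.

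- **The plan already provides self-completion.** The dietitian's task refers forward to the scale descriptions, and the GERDQ is self-administered there. A reader might infer that the two passages contradict each other, or that symptoms are reported face to face. The documents support neither: the dietitian may only hand out and collect a form. This part stands for the GERDQ. It does not settle the GSAS, and it does not change who handles either form.

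- **The bias may cancel.** All four arms receive meal plans, instruction and food lists, and no arm is described as having more contact with the dietitian. Influence common to all arms would largely drop out of between-arm comparisons. That is fair. A differential effect is plausible because the hypothesis favors particular arms, but it is not demonstrated.

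- **The fix removes only part of the problem.** Subjects know what they eat, so their own expectations remain whoever collects the form. This stands.

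- **The main inference is safe.** The only powered outcome is instrument-recorded. This also stands.

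A reader might also be tempted to put a number on the harm. Suppose reporting shifts by 0.2 SD between groups. The false-positive rate is P(|Z + 0.2/√(2/n)| > 1.96). With n = 45 per group the offset is 0.2/√(2/45) = 0.949 and the rate is 15.8%. With n = 90 per group the offset is 0.2/√(2/90) = 1.342 and the rate is 26.9%. The arithmetic is right, but the 0.2 SD is invented, no shift gives 5%, and section 10.0 specifies no such two-group test of a symptom score. Nor could the whole shift be credited to who collects the survey. These figures do not measure this weakness.

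**Conclusion.** The point holds with limited scope. One role both teaches the randomized diet and performs the symptom surveys, with no blinding or separation described. The subjective Aim 1 symptom outcomes are exposed to avoidable assessor and social-desirability influence at day 63. They are exposed at day 7 only if the survey follows randomization and diet instruction. Exposure is greatest for the GSAS.

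This rests on two readings: that the study dietitian is one role held by a person who knows the arm, and that performing the survey involves some contact over it. The size of any bias is unknown. The documents do not support extending the concern to the primary outcome or to medication use, or calling the GERDQ description a contradiction.

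This is a cheap improvement, worth making because a biased symptom report cannot be repaired in the analysis.

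**What to change.** - Have subjects complete both the GSAS and the GERDQ alone, in the same way at baseline, day 7 and day 63. Including baseline keeps the mode from changing between baseline and follow-up.
- Schedule completion before the subject meets the dietitian and, at day 7, before the envelope is opened.
- Have nursing staff already at the visit hand out and collect the forms. At the testing visits, section 6.0 already lists research-center nursing ahead of the dietitian.
- In section 6.0 (Testing Procedures), remove the GERD symptom survey from the dietitian's tasks. Under Measures (GERD Symptoms), state self-completion for both scales.
- Report the symptom results with the limitation that subjects knew their diet.

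**Cost:** a wording change and a small added task for nursing staff, with no new visit. The plan does not say whether those nurses know the arm, but self-completion makes that matter less. Separating roles looks feasible, since the Measures list already gives the diet recalls to a separate assessment core. Subject expectation bias remains.
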